8.1. Statistical Hypotheses

The Part 1 primary objectives are to evaluate the safety and tolerability of ascending multiple SC injections of BIO89-100 in subjects with NASH or who have NAFLD and at a high risk of NASH and to characterize BIO89-100 PK. No formal hypotheses will be tested for the primary objectives.

The secondary objectives of evaluating the effect of BIO89-100 on selected PD markers and biomarkers will be assessed by point estimates, 90% confidence intervals and the descriptive p-values of mean changes/percentages changes from baseline within and between treatment group.

For Part 2, the primary objectives are to evaluate incidence of AEs and to assess histological response of BIO89-100 in the NASH population.

8.2. Sample Size Determination

For Part 1, no formal sample size calculation was performed for the primary endpoint(s) as the total of approximately 83 subjects, consisting of 6:2 (Cohort 1), 12:3 (Cohort 2), 9:3 (Cohorts 4 and 6), or 14:4 (Cohorts 3 and 5) receiving active : placebo, respectively is considered adequate for Part 1 of this study and are expected to enroll to achieve study objectives.

A power assessment based on [REDACTED] subjects in a dose cohort compared to the pooled 19 placebo subjects will provide [REDACTED] power, respectively, to detect a difference in mean percentage change from baseline between treatment groups of [REDACTED], assuming the standard deviation of endpoint in each group is [REDACTED]. Calculation was based on two-sample t-test with one-sided 5% (e.g., two-sided 10%) type I error probability.

Subjects who withdraw from the study before the Day 50 assessments may be replaced at the discretion of the Sponsor.

For Part 2, no formal power calculations were used to determine the sample size in Cohort 7 and the number of subjects was chosen based on clinical experience of similar proof-of-concept histology studies and feasibility. This sample size accounts for an anticipated [REDACTED] of subjects who will not undergo the post-baseline liver biopsy (e.g., [REDACTED] to have paired liver biopsies). With a sample size of [REDACTED], the 95% confidence interval of the histological response rate would

have a half-width no greater than █ assuming the histological response █. The actual half-width will depend on the observed histological response rate.

8.3. Populations for Analyses

For purposes of analysis, the following populations are defined:

Population	Description
Screened Analysis set	All enrolled subjects who signed informed consent and undergone screening.
Part 1	
Randomized Analysis set	All enrolled subjects who are assigned a randomization number in the study. For analysis purposes, subjects will be analyzed according to the treatment they were randomized to regardless of actual treatment received.
Safety Analysis set	All randomized subjects who receive at least 1 of study intervention. In this population, subjects will be summarized based upon the study intervention actually received, regardless of the study intervention to which they were randomized.
PK Analysis set	All subjects in the Safety Analysis set who have sufficient data to adequately characterize the trough serum BIO89-100 concentrations and have no other events, or protocol violations that would adversely affect results, such as not completing the full dose. The analysis population for any population pk modeling may be defined separately in a population PK data analysis plan.
PD Analysis set	All subjects in the Safety Analysis set who have measurable post-baseline PD data; subjects will summarized based on the randomized treatment group. Different PD analysis sets may be used for different types of PD endpoints, e.g., MRI-PDFF.
Part 2	
Full Analysis Set	All enrolled subjects who received at least one dose of study intervention. Full Analysis Set will also be used for safety summary in Part 2
PK Analysis Set	All enrolled subjects in the Full Analysis Set who have sufficient data to adequately characterize the trough serum BIO89-100 concentrations and have no other events, or protocol violations that would adversely affect results, such as not completing the full dose.
PD Analysis Set	All enrolled subjects in the Full Analysis Set who have measurable post-baseline PD data. Different PD analysis sets may be used for different types of PD endpoints, e.g., MRI-PDFF.
Biopsy Analysis Set	For Cohort 7 only. All enrolled subjects in the Full Analysis Set and have both baseline and post-baseline biopsies.

8.4. Statistical Analyses

The statistical analysis plan (SAP) will be developed and finalized before database lock and will describe the subject populations to be included in the analyses, and procedures for accounting for missing, unused, and spurious data. Pooling of placebo subjects in Part 1 will be performed when applicable and will be specified in the analysis plan. This section is a summary of the planned

statistical analyses of the primary and secondary endpoints. Analysis of biomarkers and PD endpoints as well as their correlation with PK will be detailed in the SAP.

In general, summary descriptive statistics will be presented for demographics and baseline characteristics, safety endpoints, PK, and PD parameters. Descriptive statistics will include number of observations, mean, standard deviation, median, minimum, and maximum for continuous parameters. For PK and PD parameters, descriptive statistics will include the number of observations, arithmetic and geometric means, standard deviation, coefficient of variation, median, minimum, and maximum. Categorical parameters will be displayed using counts and percentages within each category.

For Part 1, while no formal hypothesis testing is planned for the primary objectives, the evaluation of potential efficacy will be determined based on the totality and pattern of data from the biomarker and PD endpoints. The assessment of biomarker and PD endpoints will employ 90% confidence intervals and significance testing for assessing within group changes and percentage changes from baseline and comparisons of the BIO89-100 doses to the pooled placebo group. Details will be provided in the SAP.

The correlation between relevant PK parameters and PD endpoints will be examined as will be detailed in the SAP.

Subjects with dose interruptions impacted by the COVID-19 pandemic will be noted in the listings. Subgroups including and excluding subjects with dose interruptions due to COVID-19 pandemic may be considered for both efficacy and safety analyses as appropriate.

For Part 2, endpoints of different histological responses will be summarized with the point estimates and 95% confidence intervals of the proportions of subjects who meet the response criteria using the biopsy analysis set.

8.4.1. Safety and Tolerability Analyses

All safety analyses will be performed on the Safety Analysis Set in Part 1 and Full Analysis Set in Part 2. The safety assessment will be based on AEs, laboratory values, concomitant medication use, ECG, vital signs, and physical examination. Summaries will be presented by treatment/dose.

All adverse events will be coded using the Medical Dictionary for Regulatory Activities (current version of MedDRA). The severity of adverse events will be graded according to the current version of National Cancer Institute (NCI) common terminology criteria for adverse events (CTCAE) v5. All AE summaries will include treatment-emergent adverse events (TEAEs), defined as those which occur after the first dose of study intervention (BIO89-100 or placebo). Treatment-related AEs are those which were determined by the Investigator to be related to study intervention. The incidence of treatment-related AEs (as recorded in the eCRF) will be summarized using descriptive statistics by system organ class (SOC) and preferred term, categorized by severity as recorded in the eCRF. Counting will be done for each subject (subjects will only be counted once within each SOC or preferred term). The frequency of TEAE (AE burden) will be summarized using descriptive statistics by SOC and preferred term (PT). Counting will be done for events (regardless of subjects), by SOC and PT. The incidence of TEAE will also be presented by time of onset post-dose, SOC, PT, and severity.

A listing of TEAEs and TEAEs leading to study discontinuation will be provided. Summaries will be presented by dose/treatment group. Subject listings of SAEs and AE leading to withdrawal will be presented. Actual values and changes in laboratory (serum chemistry, hematology, coagulation, and urinalysis), ECG, and vital signs measurements including weight data will be summarized descriptively. Laboratory data will also be presented by grading (severity) scale according to the current version of NCI CTCAE for each time point recorded. All values will be compared with prespecified boundaries to identify potentially clinically significant values or changes, as detailed in the statistical analysis plan, and such values will be listed. All prior and concomitant medications will be coded using the World Health Organization drug dictionary (WHO Drug) and will be listed. Concomitant medications will include all medications taken from first dose through to the EOS visit. If any subject dies during the study, a listing of deaths will be provided and all relevant information will be discussed in the subject narrative included in the clinical study report. The relationship of overall safety with respect to pharmacokinetics, immunogenicity assessments, and prespecified exploratory biomarkers will be evaluated, as appropriate.

The number (%) of subjects who fail to complete the study and the reason for discontinuation, and the number (%) of subjects who fail to complete the study due to related adverse events will be summarized.

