2.3.1.1. Potential Risk: Immunogenicity

As with any biologic drug, exposure to BIO89-100 may potentially provoke an immune response, with formation of ADAs, that may lead to loss of efficacy or adverse effects (e.g., hypersensitivity, loss of endogenous FGF21 activity). After single administrations to healthy subjects in study TV47948-SAD-10122, [REDACTED] of BIO89-100-treated subjects had positive ADA, all with [REDACTED] ADAs to BIO89-100 have [REDACTED] [REDACTED], without a discernible effect on PK or PD parameters that were evaluated in these studies. No severe hypersensitivity event has been reported in Cohorts 1-6 (completed). Of note, formation of ADAs in nonclinical species is expected, and is generally not considered predictive for immunogenicity in humans.

In study BIO89-100-102, the following mitigation measures will be implemented to address the potential risk of severe hypersensitivity reactions, including anaphylaxis:

- a. Subjects with any prior exposure to an FGF21 analogue, if known, will be excluded from participating in the study.
- b. In Part 1, subjects will be under observation and intensive monitoring (including multiple vital signs measurements) for 48 hours in 2 domiciled visits (1st and 5th dose for Cohorts 1-4, 1st and 3rd dose for Cohorts 5 and 6), and for 2 hours post dose during ambulatory dosing visits in the first month. In Part 2, subjects will be observed for at least 15 minutes after each dose of study intervention.
- c. All study sites will have appropriate measures (personnel and equipment) to diagnose and address severe hypersensitivity reactions, including proximity to a hospital to which a subject may be evacuated, if needed. Details on identification and management of severe hypersensitivity reactions after home administration will be provided in the Home Administration Manual.
- d. Severe hypersensitivity reactions (including anaphylaxis) will be an event to monitor.
- e. Stopping rules include serious hypersensitivity reactions to BIO89-100.
- f. Hypersensitivity-related AEs will be captured as part of the general safety assessment in all subjects.

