8. STATISTICAL CONSIDERATIONS

This section describes the statistical analysis as foreseen at the time of planning the study. Changes, additions, and further details about the analyses will be described in the statistical analysis plan, if applicable. Any subsequent additional analyses or changes to analyses that may be required will be fully disclosed in the clinical study report. Summaries and analyses will be presented by dose/treatment group for Part 1 and separately for Part 2. Before database lock, final statistical and pharmacokinetic analysis plans containing full details of all planned analyses will be produced. The analyses presented here represent an outline of the intended methodology. Details of the analysis will be described in a Statistical Analysis Plan. All clinical data will be summarized using descriptive statistics: number (n), mean, standard deviation (SD), median, minimum, and maximum for continuous measurements, and counts and percentages for categorical measurements.

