9.3.3. Definition of Events to Monitor

Sponsor-defined Events to Monitor for BIO89-100:

Events to Monitor include hypersensitivity reactions occurring after the first administration of study agent(s) in subjects participating in this clinical study. These events must be reported by the Investigator to the sponsor within 24 hours and are to be considered serious (for regulatory reporting purposes) only if they meet the definition of an SAE. The events are to be reported on an SAE form

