9.5.1. Adverse Events

All adverse events will be coded using the MedDRA (version 23.0 – Apr 2020).

The incidence and number of events of the following will be summarized by treatment and overall:

- Overall TEAE Summary*
- TEAEs by System Organ Class (SOC) and Preferred Term (PT)
- Serious TEAEs by SOC and PT
- Serious Related TEAEs by SOC and PT
- Serious TEAEs Leading to Study Discontinuation by SOC and PT
- Serious TEAEs Leading to Investigational Product Discontinuation by SOC and PT
- Related TEAEs by SOC and PT
- TEAEs Leading to Study Discontinuation by SOC and PT
- Fatal TEAE (will be provided in a listing)
- TEAEs by SOC, PT and Maximum CTCAE Grade
- TEAEs by SOC, PT and CTCAE Grade
- TEAEs Leading to Investigational Product Discontinuation by SOC and PT
- TEAEs by PT in Descending Frequency
- TEAE by SOC and PT in subgroup of Biopsy confirmed NASH (Yes if F1, F2, F3, else No) Yes/No

When calculating incidence; subjects will only be counted once per SOC, PT, or grade.

When deriving relationship of AEs to study treatment, categories with the relationship of “definitely related”, “probably related”, “possibly related” will be considered “related”. If an AE has missing relationship, it will be assumed to be related to the investigational product for analysis purposes. If an AE has missing CTCAE grade, the missing grade will be imputed as a severe grade 3 adverse event. Any TEAE related to VOCID19 will be provided in a listing.

TEAEs by System Organ Class (SOC) and Preferred Term (PT) by subgroup of biopsy confirmed NASH (Yes if F1, F2, F3, else No) will be summarized.

*In the Overall TEAE summary, the most severe CTCAE grade will be summarized for each subject.

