8.5.1. Adverse Events

All adverse events will be coded using the MedDRA (version 23.1 – Sep 2020).

The incidence and number of events of the following will be summarized:

- Overall TEAE Summary*
- TEAEs by System Organ Class (SOC) and Preferred Term (PT)
- Serious TEAEs by SOC and PT
- Serious Related TEAEs by SOC and PT
- Serious TEAEs Leading to Study Discontinuation by SOC and PT
- Serious TEAEs Leading to IP Discontinuation by SOC and PT
- Related TEAEs by SOC and PT
- TEAEs Leading to Study Discontinuation by SOC and PT
- Fatal TEAE (will be provided in a listing)
- TEAEs by SOC, PT and Maximum CTCAE Grade
- TEAEs by SOC, PT and CTCAE Grade
- TEAEs Leading to IP Discontinuation by SOC and PT
- TEAEs by PT in Descending Frequency

When calculating incidence; subjects will only be counted once per SOC, PT, or grade.

When deriving relationship of AEs to study treatment, categories with the relationship of “definitely related”, “probably related”, and “possibly related” will be considered “related”. If an AE has missing relationship, it will be assumed to be related to the IP for analysis purposes. If an AE has missing CTCAE grade, the missing grade will not be imputed. A separate category for “missing” will be included in the table. Any TEAE related to COVID19 will be provided in a listing.

*In the Overall TEAE summary, the most severe CTCAE grade will be summarized for each subject.

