8.5.7. Immunogenicity Analyses

Immunogenicity assessment will utilize a tiered approach (i.e., screen, confirm, titer, binding specificity and neutralizing activity). Results of immunogenicity assessment will be summarized by displaying the number and proportion of subjects with positive and negative tests. Antibody titers will be listed and summarized (i.e., n, mean, SD, median, min, max) by study visit.

Available binding specificity and neutralizing immunogenicity results will be listed.

9. Changes to Planned Analysis in the Protocol

There are no changes to the planned analysis in the protocol.

10. Statistical Software

All statistical analyses will be performed using SAS version 9.4 or higher.

11. References

National Heart, Lung and Blood Institute (2020). *Low Blood Pressure*. Retrieved May 19, 2020, from <https://www.nhlbi.nih.gov/health-topics/low-blood-pressure>.

12. Appendix

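### The Part 2 SAP omits the protocol's summary of TEAEs by time of onset after dosing yet declares no changes; the Part 1 SAP shows the same gap, subject to a version check

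*Protocol*

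**What the plan says.** Protocol 8.4.1 governs safety analysis for the Part 1 Safety Analysis Set and the Part 2 Full Analysis Set. Among the adverse event summaries it commits to is this one: "The incidence of TEAE will also be presented by time of onset post-dose, SOC, PT, and severity". Protocol 8 says how departures are to be handled: "Changes, additions, and further details about the analyses will be described in the statistical analysis plan, if applicable".

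Each SAP then gives a bulleted list of its adverse event tables (Part 1 SAP 9.5.1, Part 2 SAP 8.5.1). The lists cover SOC and PT, seriousness, relatedness, discontinuation and grade, for example "TEAEs by SOC, PT and Maximum CTCAE Grade", and frequency order, "TEAEs by PT in Descending Frequency". Part 1 adds a subgroup table by biopsy-confirmed NASH. Neither list has an entry for time of onset.

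The section on changes from the protocol (section 10 in Part 1, section 9 in Part 2) reads the same in both SAPs: "There are no changes to the planned analysis in the protocol".

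**The concern.** Safety and tolerability are a primary objective in both parts, and the product is an injected protein. Protocol 2.3.1.1 and 2.3.1.4 name hypersensitivity and injection site reactions as potential risks. For events of that kind, the interval between dose and onset is part of the description of the harm. It also bears on how the post-dose observation described in 2.3.1.1 is read: in Part 1, 48 hours at two domiciled visits and 2 hours after ambulatory doses in the first month; in Part 2, at least 15 minutes after each dose. Part 2 also allows dosing at home.

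A programmer who follows either SAP as written will not produce the onset summary. The no-changes statement would then tell a reader of the study report that nothing had been left out.

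**Working it through.** The plan gives no figure to reproduce. The check is a comparison of texts, with simple arithmetic for size.

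**1. Commitment against table list**

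| Dimension in Protocol 8.4.1 | Part 1 SAP 9.5.1 (14 entries) | Part 2 SAP 8.5.1 (13 entries) |
|---|---|---|
| SOC and PT | yes | yes |
| Severity | yes (grade and maximum grade) | yes (grade and maximum grade) |
| Time of onset after dosing | no | no |

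**2. Could redaction explain it?** No. Neither adverse event list carries a redaction mark, and the safety headings in the two contents lists run unbroken (9.5.1 to 9.5.7 and 8.5.1 to 8.5.7).

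**3. Which protocol does each SAP implement?** The Part 2 SAP cites Version 5.0 of 11 March 2021. The Part 1 SAP cites Version 3.0 of 25 March 2020, which is not supplied. The comparison for Part 1 is therefore with the current protocol only.

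**4. Is onset recorded and shown anywhere?** Yes. Protocol 8.4.1 plans a TEAE listing, and both SAPs (9.1.1 and 8.1.1) put all electronic data capture data into subject listings. The date-imputation rules (5.2.1 in each SAP) refer to a time of onset. Protocol 5.5 has date and time recorded for doses given in the clinic. For home doses it refers to the Home Administration Manual, which is not supplied, so whether clock time is recorded there is unknown.

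**5. Size**

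- Part 2: 20 subjects; 20 × 20 = 400 planned doses.
- Part 1 active: 6 + 12 + 14 + 9 + 14 + 9 = 64 subjects. Placebo: 2 + 3 + 4 + 3 + 4 + 3 = 19. Total 83.
- Part 1 active doses planned: 41 × 13 (QW) + 23 × 7 (Q2W) = 533 + 161 = 694.

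**6. Is the promised table fully defined?** No. The protocol does not say which dose *post-dose* refers to, and the choice decides what the table shows. Take a Part 2 event that begins on Day 134, just after the twentieth dose. Counted from the first dose, it falls at 134 − 1 = 133 days. Counted from the most recent dose, it falls on day 0. Only the second reading separates events soon after an injection from later ones.

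**The case against.** The strongest reply is that little is lost. Onset is listed for every subject, Part 2 has only 20 subjects, and the primary safety endpoints (subject incidence of TEAEs and of serious TEAEs in the Part 2 SAP, 4.1.1) are all tabulated. This stands as a limit on size. It does not remove the point, because a listing is not the incidence summary that the protocol promises, and the SAP says that nothing changed.

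A second reply is that Part 1 cannot be faulted against a protocol version that nobody here can read. That stands too, and Part 1 is qualified accordingly.

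Three stronger readings are tempting, and the documents do not support them.

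- *A reader might infer that the timing of reactions goes unreported.* It is in the listings; only the summary is missing.
- *A reader might infer that the SAPs dropped a table of Events to Monitor or of injection site reactions.* The protocol's statistical section promises neither, and 2.3.1.1 places hypersensitivity-related events within the general safety assessment. Injection site reactions are also outside the definition: "Events to Monitor include hypersensitivity reactions occurring after the first administration of study agent(s) in subjects participating in this clinical study".
- *A reader might infer that injection site reactions will be scattered over several preferred terms and their overall rate lost.* The documents do not show this. Protocol 2.3.3 already gives one pooled figure for preliminary Part 1 data, 6.3% of BIO89-100 subjects. A rate that depends on grouping is a reason to define the group in advance, not evidence of a lost analysis.

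**Conclusion.** The point holds in a narrow form. For Part 2, the SAP leaves out one safety summary that the protocol commits to, without declaring or justifying the omission. The Part 1 SAP has the same gap against the current protocol; whether it was a departure when written depends on whether Version 3.0 contained the sentence. The omission affects the completeness of safety reporting and the accuracy of the no-changes statement. It does not affect the primary safety endpoints or the underlying data.

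Two assumptions are made: that the supplied protocol is the version the Part 2 SAP cites, since the supplied text shows no version number, and that the bulleted lists are meant to be the full set of adverse event tables, as their form suggests. The point should be settled before database lock, but it is a correction to the plan and not a threat to the study's conclusions.

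**What to change.** **Main change.** Add to Part 2 SAP 8.5.1 a table of TEAE subject incidence by onset interval, SOC, PT and severity. The text should:

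- say whether *post-dose* means the first or the most recent dose;
- fix the intervals in advance;
- use date-based intervals (for example day of dose, next day, later) where home dose times are not recorded.

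Make the same addition to Part 1 SAP 9.5.1 if Version 3.0 contained the sentence.

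**Alternative.** If the sponsor does not want the table, correct the no-changes statement and give the reason for leaving it out.

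**Optional, and not a dropped protocol analysis.** Prespecify one grouped row for hypersensitivity and a separate one for injection site reactions, each subject counted once. Before the first can be programmed, two protocol passages must be reconciled. Section 2.3.1.1 says "Severe hypersensitivity reactions (including anaphylaxis) will be an event to monitor", whereas 9.3.3 is not limited to severe reactions.

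**Cost.** SAP wording and programming. Clinic dose times are already recorded under Protocol 5.5. What is recorded for home doses should be confirmed in the Home Administration Manual before the intervals are fixed.
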